3.2 Regulatory status of the study product

The active study products are already marketed as Kaneka Ubiquinol™ (Kaneka QH™ active antioxidant form of coenzyme Q10).

3.3 Selection of Subjects

3.3.1 Planned number of subjects

Sample size: 51 (17 per group), healthy, adult males and females.

In females, FMD varies with the hormonal cycle. Therefore, to avoid such complications, the study will be conducted in post-menopausal female subjects only.

Subjects will be recruited from subjects referred as outpatients to U.O.C. Laboratorio Analisi – POR I.N.R.C.A. Ancona, Italy. Selection of suitable subjects will be made according to the inclusion and exclusion criteria described in the following sections.

3.3.2 Inclusion Criteria

- Male aged 35 - 65 years (35 and 65 included).
- Post-menopausal female (without a period for more than 1 year), until 65 years (65 included).
- Subjects enrolled for primary prevention but never treated (only life style modification suggested, according guidelines).
- FMD level measured between:
2,5% < FMD baseline value < 6% (at Screening Visit).
- BMI: 18.5 - 29.9 kg/m².
- LDL Cholesterol levels between 130 and 200 mg/dl (based on previous evaluation, performed within 1 month from the Screening Visit).

3.3.3 Exclusion Criteria

- Use of any cardiovascular disease related drugs prior to Screening Visit.
- Participation in any clinical trial while participating in this trial.
- Greater than 5% change in body weight within 1 month of Screening Visit.
- Subjects playing competitive physical activity.
- Subject taking lipid-altering drug therapy within four weeks prior to Screening Visit.
Also excluded are supplements known to have significant lipid altering effects, such

as niacin (>100 mg per day), garlic (> 600 mg per day), omega-3 fatty acids (> 1 g omega-3 fatty acids per day), red yeast rice extract, phytosterols / phytosterols (> 0.5 g per day), soluble fiber (>1 g per day), chitosan (> 1 g per day) and conjugated linoleic acid (CLA; > 3 g per day).

- Subject taking any concomitant treatment with phosphodiesterase inhibitors (e.g. sildenafil citrate, tadalafil, vardenafil) and donors of NO (nitric oxide), like other long-acting derivatives of GTN (glyceryl trinitrate), such as isosorbide dinitrate and amyl or butyl nitrite.
- Excluded concurrent medications are: systemic corticosteroids (nasal and inhaled corticosteroids are permitted), orlistat, bile acid resins, no more than 1 g of prescription omega-3 fatty acids, cyclical or non-continuous hormone therapy (estrogen or testosterone).
- No more than 2 alcoholic units per day. Units are defined as 12 grams of ethanol, e.g. a small glass (125 ml) of medium gradation wine, a can of beer (330 ml) of average gradation or 40 ml dose of liquors.
- Consumption of flavonoids-enriched products.
- Consumption of vitamin C-enriched products or supplements containing vitamin C.
- Has a diagnosis of type 1 or type 2 diabetes mellitus, hepatic or renal impairment or diseases, thyroid disorders.
- Known cardiovascular disease or stroke, except for conditions that are deemed clinically insignificant by Principle Investigator or Sub-investigator, or study site physician (e.g. clinically insignificant atherosclerotic lesions observed by imaging studies).
- History of significant gastrointestinal disease such as severe constipation, diarrhea, malabsorptive disease, inflammatory bowel disease (e.g. Chron's disease, ulcerative colitis).
- History of severe psychiatric illness which in the opinion of the investigator would interfere with the optimal participation in the study.
- History of cancer within 5 years of Screening Visit (except for successfully treated basal and squamous cell carcinoma of the skin).
- Known HIV seropositivity.
- History of bariatric surgery.

- Allergic to the test products or placebo.
- Smokers > 10 cigarettes/day.
- Individuals who in the opinion of the principal investigator have a risk of non-compliance to the study procedures or who are otherwise not appropriate to include in this clinical trial.

3.3.4 Dietary Restrictions

- Subjects will be asked not to consume supplements known to have significant lipid altering effects, from the start to the end of the study, such as niacin (>100 mg per day), garlic (> 600 mg per day), omega-3 fatty acids (> 1 g omega-3 fatty acids per day), red yeast rice extract, phytosterols / phytosterols (> 0.5 g per day), soluble fiber (>1 g per day), chitosan (> 1 g per day) and conjugated linoleic acid (CLA; > 3 g per day) or flavonoids-enriched products.
- Subjects will be allowed to drink no more than 2 alcoholic units per day from the start to the end of the study. Units are defined as 12 grams of ethanol, e.g. a small glass (125 ml) of medium gradation wine, a can of beer (330 ml) of average gradation or 40 ml dose of liquors.
- Subjects are not allowed to consume any other ubiquinol / ubiquinone supplement from the start to the end of the study.
- Subjects are not allowed to consume vitamin C supplements from the start to the end of the study.

3.4 Randomization Procedure

A simple randomization technique, i.e. a randomization based on a single sequence of random assignments, will be used. A computer-generated random numbers list will be used and subjects will be assigned a number according to their order of inclusion in the study.

According to the technique above outlined, 51 subjects will be randomly allocated to one of the 3 study groups; treatments will be randomised to subject numbers (1-51).

Randomized subjects who are withdrawn from the study after receiving at least one dose of study product will not be replaced.

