METHODOLOGY AND STUDY DESIGN	
Double-blind, randomized, placebo – controlled, parallel groups clinical study with 3 intervention groups to be carried out on 51 subjects.
 
Three visits will be envisaged to the test facility: a Screening Visit and 2 Measurement Visits will be performed, each lasting approximately 1 hour. There will be 4 weeks between each visit.
 
At each Visit subjects should have to:
 
 • ≥12-h overnight fast • Avoid caffeine for 72h • Avoid high-fat food the day before • Avoid tobacco for at least 4-6h before • Abstain from exercise for >12h before the test 
During Screening Visit the eligibility criteria will be verified and, if fulfilled, each subject will be randomized to one of the 3 study groups after signing the Informed Consent Form.
 
During each visit a short physical examination will be performed and a blood sample will be collected from the vein in the left arm to evaluate CoQ10 levels (red / ox CoQ10 levels) and levels of the markers of oxidative stress. After acclimatisation and rest for ≥ 30 minutes blood pressure (triplicate, first discarded) and FMD (baseline or Week 4 and 8 measurement) will be measured.
 
At Screening Visit and at Week 4, subjects will receive the assigned test product (according to randomization) for consumption at home during the coming 4 weeks and leave the facility.

PRODUCT TO BE TESTED	
 • GROUP A: Ubiquinol (200 mg daily) • GROUP B: Ubiquinol (100 mg daily) • GROUP C: matched placebo
DURATION OF TREATMENT	Total duration of treatment will be 8 weeks.

SAMPLE SIZE	Fifty-one subjects, considering a 20% dropout rate, are a sample size considered as appropriate for this study (17 for each group).
INCLUSION CRITERIA	
This study will include male and post-menopausal female subjects.
 
 • Male aged 35 - 65 years (35 and 65 included). • Post-menopausal female (without a period for more than 1 year), until 65 years (65 included). • Subjects enrolled for primary prevention but never treated (only life style modification suggested, according guidelines). • FMD level measured between: 2,5% < FMD baseline value < 6% (at Screening Visit). • BMI: 18.5 - 29.9 kg/m². • LDL Cholesterol levels between 130 and 200 mg/dl (based on previous evaluation, performed within 1 month from the Screening Visit).

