6.1 Sample Size Calculation

Sample size calculation is carried out with use of G*power Software.

The parameters used to compute sample size for this study were taken from the reference article by Gao et al 2012, a meta-analysis of 5 randomized controlled trials.

Mean and SD taken from the article by Watts GF et al 2002, one of the RCT mentioned in reference article (see fig. 2 in the article by Gao et al), were considered as appropriate values to be taken into account: considering group one mean and SD as 1.6 (1.16) and second group mean and SD as -0.4 (2.24), with 80% power and 5% two-sided significance level, 14 subjects are required for one group.

In this study, considering a 20% dropout rate, a total of 52.5 subjects should have been enrolled; a sample size equal to 51 subjects was deemed as appropriate.

It is to be noted that in this study the minimum increment of FMD reached with the number of patients provided for each group is to be considered as equal to 1.6% (according to Figure 2 shown in Gao et al, in particular by referring to the study of Watts, which provides a sample size similar to ours).

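### Simple randomisation, as section 3.4 words it, does not secure the 17 subjects per group stated elsewhere; the average cost is small, but the passages conflict and the fix is nearly free

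*Protocol*

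**What the plan says.** Section 3.4 names and defines the method: "A simple randomization technique, i.e. a randomization based on a single sequence of random assignments, will be used". It adds: "A computer-generated random numbers list will be used and subjects will be assigned a number according to their order of inclusion in the study", and then that "51 subjects will be randomly allocated to one of the 3 study groups; treatments will be randomised to subject numbers (1-51"). It mentions no block, stratum, allocation ratio or fixed arm total. It also closes off later repair of arm sizes: "Randomized subjects who are withdrawn from the study after receiving at least one dose of study product will not be replaced".

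The arm size is stated in two other places. Section 3.3.1 has "Sample size: 51 (17 per group), healthy, adult males and females", and the sample-size entry of the synopsis says that fifty-one subjects "are a sample size considered as appropriate for this study (17 for each group").

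Section 6.1 carries the power argument: "considering group one mean and SD as 1.6 (1.16) and second group mean and SD as -0.4 (2.24"), at 80% power and 5% two-sided significance, "14 subjects are required for one group". With 20% drop-out the total comes to 52.5, which the protocol sets at 51.

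**The concern.** Under simple randomisation each subject is allocated independently of the others, so arm sizes are random. Seventeen per group is then the expected size of each arm, but the scheme does not deliver it. An analysis plan written later cannot mend this, because the list is made before the first subject enters and the protocol itself fixes the method.

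Precision and the test's error rate are both at stake. The design has no slack: the total was rounded down from 52.5 to 51, and withdrawals after a first dose are not replaced. Placebo enters both primary comparisons, so a short placebo arm weakens both. Section 6.1 also assumes a much larger SD in one group than in the other. One-way ANOVA, which section 6.3 plans for normal data, is sensitive to unequal variances when the group with the larger variance is also the smaller one.

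**Working it through.** **Inputs.** From section 3.4: N = 51, three arms. From section 6.1: means 1.6 and −0.4, SDs 1.16 and 2.24, two-sided α = 0.05, power 80%, drop-out 20%. Assumed: probability 1/3 per arm, inferred from 17 per group because no ratio is stated.

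**1. The protocol's own figure.** Difference = 1.6 − (−0.4) = 2.0. Pooled SD = √[(1.16² + 2.24²)/2] = 1.784, so d = 2.0/1.784 = 1.121. Two-sample t-test power (noncentral t) is 78.3% at 13 per group and 81.5% at 14 per group, so 14 is reproduced. Total: 3 × 14/(1 − 0.20) = 52.5, also reproduced.

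**2. Arm sizes under simple randomisation.** The sizes follow a multinomial(51; 1/3, 1/3, 1/3) distribution.
- SD of one arm's size = √(51 × 1/3 × 2/3) = 3.37, around a mean of 17.
- P(17/17/17) = 51!/[(17!)³ × 3⁵¹] = 0.0160, about 1 list in 62.
- Expected smallest arm = 13.6 (exact enumeration).

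| Event before drop-out | Probability |
|---|---|
| At least one arm ≤ 13 | 43.4% |
| At least one arm ≤ 12 | 26.2% |
| At least one arm ≤ 10 | 7.0% |
| A named arm, e.g. placebo, ≤ 13 | 14.9% |
| Largest minus smallest arm ≥ 8 | 41.1% |

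**3. Power for one active arm against placebo.** The difference is 2.0 and the pooled SD 1.784. Multiplying each arm by 0.8 for drop-out:
- balanced, 17 × 0.8 = 13.6 per arm: 80.3%;
- simple randomisation, averaged over lists: 78.6%, a loss of 80.3 − 78.6 = 1.7 points;
- 5th percentile over lists: 69.7%, so about 1 list in 20 falls below 70%.

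If drop-out is itself random at 20% per subject, average power is 78.0% (simple) against 79.7% (fixed at 17), the same gap. The chance that some arm ends with 10 or fewer completers is 45.9% (simple) against 10.9% (fixed at 17).

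**4. One-way ANOVA type I error.** Simulated with normal data, equal means, and SDs 1.16, 1.16 and 2.24. The larger SD belongs to placebo. Giving both active arms 1.16 is an assumption, since section 6.1 describes only two groups. The nominal level is 5%.

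| Active / active / placebo | Type I error |
|---|---|
| 17 / 17 / 17 | about 6% |
| 19 / 19 / 13 | about 9% |
| 20 / 20 / 11 | about 11% |
| 15 / 15 / 21 | about 4% |

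Averaged over lists from simple randomisation the rate is about 6.4%, close to the balanced figure.

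**The case against.** The best defence is that section 3.4 may mean something else. Randomising treatments to subject numbers 1–51, read with 17 per group, could describe a list with 17 entries per arm put in random order. That is also one sequence, and it gives exactly 17 each if all 51 enter. The reading is possible, but the protocol does not state it, and its chosen term and definition describe the unrestricted scheme. If fixed totals were meant, the wording of section 3.4 is wrong and still has to change.

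The second defence is that simple randomisation is valid and unbiased, and that the average loss is under two points of power. That stands in full.

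Four stronger conclusions might be inferred, and the documents do not support them.
- *That the placebo arm will be short in 43% of lists.* That figure is for any of the three arms; for placebo it is 15%.
- *That the scheme generally inflates the ANOVA error rate.* A small placebo arm raises it and a large one lowers it; on average the rate barely moves. Section 6.3 also provides Kruskal-Wallis for non-normal data.
- *That randomisation should be stratified by sex.* Section 3.3.1 raises the hormonal cycle and deals with it by admitting only post-menopausal women. Nothing says that FMD or its response differs between these women and men, and no sex split is given. Incomplete blocks within sex strata could also prevent exactly 17 per arm.
- *That fixing arms at 17 would secure 14 evaluable each.* It would not: 17 × 0.8 = 13.6. With arms fixed at 17 and random 20% drop-out, the chance that some arm ends below 14 is still about 83%, against 96% under simple randomisation. Most of that shortfall comes from the sample size itself.

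**Conclusion.** The point holds as a conflict of wording with a modest statistical cost. The scheme named in section 3.4 does not secure the 17 per group stated in the synopsis and section 3.3.1. Read literally, it yields that split about once in 62 lists, and in more than four lists in ten it leaves at least one arm below the protocol's own requirement of 14 before anyone drops out.

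The expected loss, about 1.7 points of power per comparison, is too small to threaten the trial. The reason to act is the tail: an unlucky list with one thin arm, or a thin placebo arm that costs precision in both primary comparisons and takes the ANOVA error rate to about 9% or more.

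These figures rest on allocation probabilities of 1/3, the means and SDs of section 6.1, 20% drop-out in every arm, and, for the ANOVA figures, an SD of 1.16 in both active arms. The change should be made, but the validity of the trial does not depend on it.

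**What to change.** Replace the first sentence of section 3.4 with wording such as: *Subjects will be allocated 1:1:1 from a computer-generated permuted-block list with block sizes varied at random (for example 3 and 6), totalling 17 per arm. The list will be held only by the independent pharmacy custodian, and block sizes will not be disclosed to site staff.* Blocks of 3 and 6 can fill 51 exactly; for example, 5 × 3 + 6 × 6 = 51.

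If a single random ordering of 17 entries per arm was intended, the minimum correction is to say so and delete the term "simple" and its definition. Blocking has the further merit of keeping the arms close if recruitment stops short of 51.

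The cost is one sentence and one new list before the first subject, with no extra subjects. The drawback is slight predictability at the end of a block. Varied block sizes, the double blind of section 3.5 and the independent dispensing in section 4.4 limit it. The shortfall of 13.6 against 14 evaluable per arm is not cured by this change and needs to be settled separately in section 6.1.

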3.5 Blinding

This will be a double blind study; the assessors will be blinded. The placebo capsules will be equal in colour, shape and weight to study products capsules (ubiquinol, provided as softgel capsules) but without active ingredients.

3.6 Withdrawal of Subjects.

Subjects may discontinue from the study at any time. In addition, the Principal Investigator (PI) or his/her designee has the right to withdraw a subject for any reason that is in the best interests of the subject. Whenever a subject is withdrawn from a study, an early withdrawal assessment must be completed stating the reason for withdrawal, assessing any eventual AE and taking other necessary assessments if needed. Withdrawals due to non-attendance must be followed up to attempt to obtain the reason that the subject is "lost to follow up".

3.7 Protocol deviations and violations

A protocol violation or deviation is any failure to comply with the protocol. All the protocol violations / deviations are required to be reported in the CRF by the investigator.

Protocol deviations

- minor

- misuse of study product not affecting compliance (e.g. missed more than three times in total; study product not taken at proper time);
- 1 day of product missed;
- a visit is delayed or anticipated for 1 day from the initially scheduled visit (if study product consumption is not affected);
- no return of unused study product;
- minor lack of compliance with restricted diet to be followed (e.g. consumed more than 2 units of ethanol per day once or twice).

- major

- no fasting state at the arrival to the study center;
- major lack of compliance with restricted diet to be followed (consumed ethanol several times (> 2) in significant quantities);
- three consecutive times and four or more non-consecutive times of product missed;

- a visit is delayed or anticipated for more than 1 day from the initially scheduled visit (even if study product consumption is not affected);
- not complying with instructions given by the study personnel.

Protocol violations (minor/major according to Sponsor's decision on a case-by-case basis)

- informed consent obtaining process not adequately performed;
- violation of inclusion / exclusion criteria;
- use of prohibited concomitant medications (i.e. taking prescribed drugs or OTCs or dietary supplement that can influence FMD);
- required tests and sampling procedures incorrectly performed or not performed at all (e.g. samples not collected);
- any other GCP non compliance.

Both minor and major protocol deviations / violations will be recorded in the Case Report Form (CRF) and will be addressed in the blind review performed before the de-blinding and statistical analysis. In case of the violation or the deviation may affect the study results (this decision will be taken according to Sponsor's decision) the subject will be withdrawn from the Per Protocol statistical analysis.

3.8 Endpoints

3.8.1 Assessment of Effects

Measurement will be taken by sonographers who have been trained to measure FMD. Subjects will be invited to study site as per randomisation schedule. After collection of the blood sample from the left arm, they will be allowed to get acclimatized at study site (temp 20-22 °C) for 30 minutes. During this time, they will be given instructions about the measurement and their blood pressure will be measured (3 individual measurements, the first discarded). After at least 30 minutes rest, they will be taken to the bed and will be asked to rest while the arm support will be adjusted and the probe and occlusion cuff will be fitted to their arm.

Each FMD measurement cycle will have the following steps and will take approximately 30 minutes:

- Subjects rests comfortably on the equipment side bed

- Right arm of the subject is partially immobilized and brachial artery is focussed
- Operator waits for 1 minute after the image on screen gets stabilised
- FMD measurement including the following steps:
 - 1-minute base scan to measure the baseline diameter of artery (Resting stage)
 - 5 minutes of forearm occlusion at 300 ± 30 mmHg (cuff occlusion stage), just below the elbow (2-5 cm from antecubital crease)
 - 4 minutes FMD scan, which will start immediately after release of occlusion (reactive hyperaemia stage)
 - When the artery has returned to baseline a second 1-minute scan is taken
- FMD will be calculated as maximal percent increase in diameter above baseline (mean value of measures obtained during 1 minute before cuff inflation). In case of an unusable baseline diameter, the expert assessing the scans can use alternative options to determine the baseline diameter (recovery diameter) as rescue option.

In the blood sample triglycerides and glucose in blood will be used to detect subjects who were not fasted. Highly sensitive C-reactive protein will be measured to assess inflammatory status. Inflammation and food intake may affect FMD but it is not anticipated that the intervention will affect these laboratory values.

Red / ox CoQ10 levels will be measured.

3.8.2 Blood sample collection

To collect blood and to perform the analysis standard methodologies will be used. On collected blood sample will not be performed genetic tests, but they will be collected only as regards what described in the study protocol and they will be destroyed at the end of the study.

3.8.3 Assessment of Safety

Safety and tolerability will be assessed by monitoring adverse events (AEs) during the whole study period. Adverse events are any untoward medical occurrence, whether or not related to study product or study procedures. AEs will be coded using ICD-9.

Ubiquinol is usually well tolerated, and cases of overdose are not known. Rarely, it may cause mild gastrointestinal upset, decrease in appetite, nausea, vomiting, diarrhoea or constipation and rash. CoQ10 may be contra-indicated for individuals taking blood thinning medication.

3.9 Concomitant medication

Any concomitant medication, including prophylactic treatments, OTC medication and all food supplements, should be reported in the subject diaries and will be entered in the case report form (CRF).

3.10 Excluded medication

Subjects on prescribed medication (including prophylactic treatments) will not be selected for the study. Any subject that will start taking prescribed medication during the study, which, in the Investigator opinion may interfere in the study, will be excluded.

Regular intake of OTC (Over-The-Counter) medication and consumption of nutritional supplement is allowed if an effect on vascular function is not expected as judged by the PI or his/her designee at screening.

Occasional intake of drugs or supplements will be evaluated during a blind review at the end of the study and may lead to exclusion from the per protocol analyses.

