6.2 Definition of Analysis Population

All subjects receiving at least one study product will be used for safety analyses. All subjects with at least 1 FMD measurements will be part of the intention-to-treat population. All subjects with no major deviation from the protocol will form the per-protocol population. All FMD measurements with acceptable quality will be used for analyses. Decision on the per-protocol population and FMD measurement quality will be made during blind review and documented.

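### Section 3.10 excludes a randomised subject who starts an interfering prescription, section 3.7 sends the same event to a per-protocol decision, and no Week 8 FMD is required after exclusion

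*Protocol*

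**What the plan says.** **Section 3.10** has two rules on medication taken during the study. For newly started prescriptions, it says of any subject who begins prescribed medication during the study: "which, in the Investigator opinion may interfere in the study, will be excluded". For occasional drugs or supplements, intake is assessed at blind review and "may lead to exclusion from the per protocol analyses".

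**Section 3.7** lists the use of prohibited concomitant medication, including prescribed drugs that can influence FMD, among protocol violations. These are recorded in the CRF and taken to blind review. If the sponsor decides that the results may be affected, the subject leaves the per-protocol analysis. No other consequence is given.

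**Section 3.6** adds that the principal investigator or designee "has the right to withdraw a subject for any reason that is in the best interests of the subject". At withdrawal, "an early withdrawal assessment must be completed stating the reason for withdrawal, assessing any eventual AE and taking other necessary assessments if needed". FMD is not named, and the section does not distinguish stopping the product from leaving the study. **Section 3.4** adds: "Randomized subjects who are withdrawn from the study after receiving at least one dose of study product will not be replaced".

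**Section 6.2** says: "All subjects with at least 1 FMD measurements will be part of the intention-to-treat population". **Section 6.4** promises both an ITT and a per-protocol analysis. The primary endpoint (section 2) is the change in FMD at Week 8.

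**The concern.** One event, starting a prescribed drug that could affect FMD, has two different consequences. Under 3.7 the sponsor decides at blind review, and only the per-protocol set is affected. Under 3.10 the investigator decides while the study is running, and the subject is excluded.

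The difference matters because the event comes after randomisation. Consent, randomisation and first supply all take place at Visit 0, so a prescription started during the study is started by a randomised subject. If that subject leaves follow-up, the Week 8 scan is probably lost. An ITT label attached to a baseline scan does not bring it back, and a statistical analysis plan can choose a missing-data method but cannot recover a measurement that was not taken.

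The loss need not be random. New prescriptions may follow blood pressure, lipids or tolerability. Blood pressure and LDL cholesterol are measured at every visit (3.11), and section 1.2 credits CoQ10 with lowering blood pressure.

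**Working it through.** **1. The rules side by side**

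| | 3.10, new prescription | 3.10, occasional intake | 3.7, prohibited medication |
|---|---|---|---|
| Who decides | Investigator | Blind review | Sponsor |
| When | During the study (natural reading) | End of study | Blind review before unblinding |
| Consequence | Excluded, from what not stated | Possible removal from per-protocol analyses | Possible removal from per-protocol analysis |

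The first and third columns can describe the same event. Section 3.10 names the per-protocol analyses where it means them, so the bare word *excluded* most naturally means out of the study. That is an inference, not a statement in the text.

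**2. What an excluded subject contributes.** Section 6.3 compares Measurements 3 vs 1, 2 vs 1 and 3 vs 2.

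- Excluded before Week 4, with no further scan: baseline only. The subject is ITT under 6.2 and enters none of the three comparisons.
- Excluded after the Week 4 scan: enters 2 vs 1 (a secondary endpoint) but not 3 vs 1 (the primary endpoint).

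**3. The plan's own sample size.** Inputs from section 6.1: means 1.6 and −0.4, SDs 1.16 and 2.24, two-sided 5%, power 80%, dropout 20%.

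- Pooled SD = √((1.16² + 2.24²)/2) = √3.1816 = 1.784.
- Standardised difference = 2.0/1.784 = 1.121.
- Two-sample t-test (noncentral t): n = 13.52, so 14 per group, as stated.
- 3 × 14 = 42, and 42/0.8 = 52.5, as stated. The plan uses 51, or 17 per group.

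**4. Weight of one subject and the reserve**

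- One subject is 1/17 = 5.9% of a planned arm.
- After 20% loss, 17 × 0.8 = 13.6 per arm remain. Power for one pairwise comparison is then about 80.3%.
- With equal numbers per arm, power is 81.5% at 14, 78.3% at 13, 74.7% at 12 and 70.6% at 11.

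The dropout allowance is therefore almost fully used in reaching 80%. It covers lost numbers, not selective loss.

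**5. Effect of one missing value on an arm mean.** Mean of those who stay minus mean of the full arm = (1/17) × g, where g is the gap between the remaining subjects' mean change and the missing subject's change. The documents give no value for g. If g is assumed to be 1 to 2 FMD points, the shift is 0.06 to 0.12 points, or 3% to 6% of the planned 2.0. The documents do not say how many subjects would be excluded or in which arms, so no total bias can be derived.

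**The case against.** **The word may be loose.** *Excluded* in 3.10 could be shorthand for the consequence in 3.7, in which case the concern about ITT mostly falls away. This reading is possible. It is less natural, because 3.10 names the per-protocol analyses separately, and even then the two sections need reconciling.

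**A Week 8 scan is not ruled out.** A reader might infer that withdrawn subjects will have no Week 8 FMD. The protocol does not say so. Section 3.6 leaves other assessments open, and nothing bars a later visit. What stands is narrower: no passage requires or schedules the scan.

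**Few subjects would be affected.** Subjects on prescribed medication are not selected (3.10), the sample is described as healthy (3.3.1), and treatment lasts 8 weeks. This stands, and it limits the size of the point.

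**Blinding protects the decision.** Site staff are blinded (4.4) and scans are read by a blinded expert (section 7), so an investigator cannot knowingly exclude by arm. That stands as far as it goes. The events that prompt a prescription can still differ by arm.

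**The 20% allowance covers loss.** It does so for numbers only, as shown in the working.

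**Conclusion.** The concern holds as a conflict between 3.10 and 3.7 and a gap in 3.6. If 3.10 is followed on its natural reading, primary-endpoint data on a randomised subject can be lost through an individual judgement made after randomisation. The ITT analysis in 6.4 then becomes, for such subjects, a comparison of those who stayed.

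The size is about 6% of a planned arm per subject, with a frequency that is unknown and probably low. A reader might go further and infer that the ITT result will be materially biased, for example by treating the whole 20% dropout as selective loss in one arm. The documents do not support that. The 20% is an all-cause planning figure, and nothing ties it to this rule, to one arm or to poor responders.

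The verdict rests on two assumptions: that *excluded* means removed from the study, and that sites take no scan which the protocol does not ask for. It is a point that should be corrected because the correction is cheap, not because a large distortion has been shown.

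**What to change.** - **Section 3.10:** say what *excluded* refers to and align it with 3.7. Starting an interfering medication is recorded, goes to blind review for a per-protocol decision, and does not remove the subject from follow-up or from ITT.
- **Section 3.6:** separate stopping the product from leaving the study. Ask subjects who stop the product, and who consent, to attend the already scheduled Week 4 and Week 8 FMD visits.

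Whether a subject continues the product after starting another medication is a clinical decision, and nothing is proposed on it.

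The cost is wording in two sections, put through the ethics approval that section 9 requires for amendments. The visits and scans are already in the schedule. The small downside is that a few scans will be taken off product or on other medication; the per-protocol decision at blind review can deal with those.
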